1 RESEARCH REFERENCE NUMBERS

Table 1: Research Reference number

| Sponsor Protocol Number: | PID: AH23-10-003 | |
|----------------------------|--|--|
| Clinical Trials Unit (CTU) | OCTRU0403 | |
| Reference: | OCTR00403 | |
| Funder Reference(s): | NIHR152309 | |
| Ethics Reference Number: | 24/WM/0157 | |
| IRAS Number: | 318800 | |
| Registry: | International Standard Randomised Controlled Trial Number (ISRCTN): ISRCTN83315571 | |
| CPMS ID: | 53594 | |

5 LAY SUMMARY/PLAIN ENGLISH SUMMARY

Perthes' disease is a rare condition of the hip joint and one of the most disabling conditions affecting children. It has a profound impact on the life of the child, and that of their family.

The hip is a 'ball and socket' joint. This can be thought of as a scoop of ice-cream, with the ice-cream (the 'ball') sitting in an ice-cream scoop (the 'socket'). Perthes' disease is caused by a problem with the blood supply to the hip, which means the ball doesn't get enough oxygen and nutrients to grow. When this happens, the hip loses its strength and flattens - like the ice-cream melting and becoming squashed. In Perthes' disease there is a temporary loss of blood supply, which means that after some months the nutrients return, and the ball again hardens. However, the bone remains whatever shape it was when it became squashed. This can lead to a ball that doesn't fit well into the socket, which can cause pain, limitation to usual activities and severe hip arthritis in childhood.

About half of the surgeons in the UK currently believe that surgery can be helpful in 'controlling' the way that the ball of the hip flattens, which could result in a better shaped hip and better outcomes for children. Surgery involves breaking the bone to re-orientate the ball to ensure that it deforms in a controlled way into the socket (called 'containment' surgery). The other half of surgeons do not undertake surgery, instead focusing on a package of care (called 'non-surgical or active containment') that involves physiotherapy, activity restriction and pain relief. Physiotherapy aims to maintain movement of the hip and keep the soft ball moving within the socket, allowing it to continually smooth its shape – i.e. the 'ice cream rolling within the scoop'. These surgeons believe that surgical containment is no better than active containment with the benefit that active containment does not expose the child to the unnecessary risks associated with surgery.

Given how disabling Perthes' disease is, and the differences in how it is treated, patients, families, and health professionals ranked the management of Perthes' disease in the top-five most important research priorities in children's orthopaedic surgery.

This study will compare children having 'containment surgery' to children having 'active containment' and specifically look at how well children are able to take part in activities three-years after joining the study.

216 children aged five years to twelve years inclusive with newly diagnosed Perthes' disease will be invited to take part in the study. Those who join will be split fairly into two groups, using a process called 'randomisation'.

At the end of the study, we aim to know if containment surgery is better than active containment for helping patients with Perthes' disease to be able to take part in activities.

6 STUDY SYNOPSIS

Table 4: Study Synopsis

| Full Study Title: OP Non-STOP Study (Operative or Non-Surgical Treatment | | | |
|--|---|--|--|
| | disease). A multi-centre prospective randomised superiority trial of | | |
| | containment surgery compared to optimised non-surgical care for | | |
| | Perthes' disease of the hip in children | | |
| Short Title: | Operative or Non-Surgical Treatment of Perthes' disease | | |
| Study Acronym: | OP Non-STOP | | |
| Study Design: | The OP Non-STOP study is a multi-centre, two arm, parallel design, | | |
| | superiority, randomised controlled clinical study. | | |
| Study Aim | To evaluate the clinical and cost-effectiveness of containment surgery | | |
| | compared to best conservative care amongst children aged 5 to 12 | | |
| | years old with Perthes' disease of the hip. | | |
| Study Participants/ | The OP Non-STOP study will recruit 216 children aged 5 to 12 years | | |
| Target Population: | inclusive with newly diagnosed Perthes' disease. | | |
| | Refer to section 11 of the main body of the protocol for full eligibility | | |
| | criteria | | |
| No. of study arms: | Two | | |
| Intervention: | Containment surgery | | |
| | In this pragmatic study the surgeon should use the containment | | |
| | procedure that is familiar to them as per their usual practice (typically | | |
| | a femoral varus osteotomy, Salter osteotomy or shelf osteotomy). | | |
| Comparator: | Optimised Non-Surgical (active) Containment – The Non-STOP Package | | |
| | (Non-Surgical Treatment of Perthes' disease) | | |
| | Children and families will receive an individual face-to-face best | | |
| | practice therapy session of up to 90 minutes with a study-trained | | |
| | physiotherapist at the recruiting hospital/regional specialist centre. | | |
| Planned Sample Size: | 216 participants | | |
| Target no. of research | 15 recruiting sites in the internal pilot increasing to a minimum of 28 | | |
| sites: | recruiting sites for the main study. | | |
| Countries of | United Kingdom (UK) | | |
| recruitment: | | | |
| Study duration: | 66 months | | |
| Planned recruitment | Recruitment is expected to last for 30 months. | | |
| duration: | | | |
| | | | |

| Duration of | Each intervention in the study is a one-time intervention – surgery or | | |
|---|---|--|--|
| intervention: | the best practice conservative therapy session. | | |
| Follow-up duration: | Each participant will be followed up for 36 months from randomisation. Consent will be sought at recruitment to share details with the Non-Arthroplasty Hip Registry (NAHR) to enable long term follow up. | | |
| | Objective Outcome Measure | | |
| Primary objective and outcome measure: | To determine whether children treated with containment surgery have better lower extremity function than children treated with active containment | | |
| Additional objectives and outcome measures: | Refer to the OBJECTIVES AND OUTCOME MEASURES section of the protocol main body for full study objectives and outcome measures. | | |

7 ABBREVIATIONS

Table 5: Abbreviations

| AE | Adverse Event | | |
|---|---|--|--|
| BOSS | British Orthopaedic Surgery Surveillance | | |
| CAT | Computer Adaptive Test | | |
| CHEERS | Consolidated Health Economic Evaluation Reporting Standards | | |
| CI | Chief Investigator | | |
| COS | Chief Investigator Core Outcome Set | | |
| COSMIN | Consensus-based standards for the selection of health measurement | | |
| COSIVIIIV | instruments | | |
| CRF | Case Report Form | | |
| CTU | Clinical Trials Unit | | |
| DSMC | Data and Safety Monitoring Committee | | |
| GCP | Good Clinical Practice | | |
| HCRW | Health and Care Research Wales | | |
| HRA | Health Research Authority | | |
| HTA | Health Technology Assessment | | |
| ICER | Incremental cost-effectiveness ratio | | |
| ICF | Informed Consent Form | | |
| ISF | Investigator Site File | | |
| ISRCTN | International Standard Randomised Controlled Trials Number | | |
| MCID | | | |
| NAHR | Minimum clinically important difference | | |
| NAHR Non-Arthroplasty Hip Registry NHS National Health Service | | | |
| NIH US National Institute for Health | | | |
| NIHR National Institute for Health and Care Research | | | |
| OCTRU Oxford Clinical Trials Research Unit | | | |
| PACS | Picture Archiving and Communication System | | |
| PI | Principal Investigator | | |
| PIS | Patient information sheet | | |
| PPI | Patient and Public Involvement | | |
| PROMIS | Patient-Reported Outcomes Measurement Information System | | |
| QALY | Quality-adjusted life-years | | |
| REC | Research Ethics Committee | | |
| SAE | Serious Adverse Event | | |
| SAP | Statistical Analysis Plan | | |
| SD | Standard Deviation | | |
| SOP Standard Deviation SOP Standard Operating Procedure | | | |
| STOP | Surgical Treatment Of Perthes' | | |
| TIDIER | | | |
| TMF | Trial Master File | | |
| TMG | Trial Management Group | | |
| TSC | Trial Steering Committee | | |
| UK | United Kingdom | | |
| | Young Persons Advisory Group | | |
| YPAG | Toung reisons Auvisory Group | | |

Note: Throughout this protocol 'parents' is used as an inclusive term for parent/guardian/carer; 'family' is used as in inclusive term for parent/guardian/carer AND the child and "child" is used as an inclusive term for child/legal ward.

8 BACKGROUND INFORMATION AND RATIONALE

8.1 Background

Perthes' disease is an idiopathic avascular necrosis in a developing femoral head (ball of the hip joint). It occurs predominantly in males (male:female ratio 4:1) between 4 and 12 years old [1, 2]. The disease results in collapse of the bone within the femoral head, which results in severe pain and disability amongst affected children. Severe pain and disability continues until the hip re-ossifies; which is typically after 2-3 years [3]. Perthes' disease typically results in long-term deformity of the hip, which can cause longer term pain and disability and is a major precipitant of premature osteoarthritis; frequently necessitating a hip replacement in early adulthood [4]. Perthes' disease is one of the most common and most poorly understood disorders encountered by children's orthopaedic surgeons.

The UK has the highest incidence of Perthes' disease in the world, with children in Northern England, and particularly Liverpool, having the greatest risk of disease [2, 5, 6]. The lifetime cumulative risk of disease in the UK is around 1:1200 children, with around 500 new cases in the UK each year [6]. The origins of the disease are very closely linked to socioeconomic deprivation [2, 6, 7], though the aetiology and mechanism are unknown.

A key principle of Perthes' disease treatment is a process called 'containment'. As the head of the femur collapses, the belief is that it should be 'contained' within the acetabulum in order to allow it to re-ossify (re-develop) in the round shape of the acetabulum. Some surgeons perform surgery to facilitate 'containment' by redirecting the femoral head into the acetabulum (i.e. a femoral osteotomy, typically with a plate & screws and a 'spica' plaster cast) and others will direct/alter the shape of the acetabulum to better cover the femoral head (i.e. pelvic osteotomy, typically with internal wires and a 'spica' plaster cast); soft tissue releases (i.e. tendon releases) may also be performed to improve the range of movement. However, other surgeons believe that a package of care including physiotherapy, activity restriction and pain relief is equally as good at achieving 'containment'; called 'active containment'. This causes international controversy and uncertainty for children and their parents/carers.

8.2 Current practice – The British Orthopaedic Surgery Surveillance (BOSS) Study

Given the controversy, there is substantial variation in the treatment of Perthes' disease. This varies from observation without any intervention, to physiotherapy involving activity restrictions and physiotherapy, to surgery involving femoral and/or pelvic osteotomies [3, 8, 9]. Over the last 6 years, researchers in the UK, including the CI of this study, have carefully explored current practice through a nationwide collaboration with the support of parent co-investigators.

In 2016, the National Institute for Health and Care Research (NIHR) funded British Orthopaedic Surgery Surveillance (BOSS) Study, was the first UK study to investigate Perthes' disease [3]. This was a cohort study of incident cases of Perthes' disease. The study collected surgeon reported outcomes on all new cases of Perthes' disease from most children's orthopaedic surgeons in the UK over an 18-month period.

371 children (396 hips) with Perthes' disease were recruited during this time. Two thirds of cases were considered eligible for surgery, and half of these received operative 'containment surgery'. The decision for surgery was almost exclusively driven by the belief and recommendation of the surgeon; with some centres offering and undertaking surgery on the majority of children, whilst other centres did not offer surgery to any. Physiotherapy and advice regarding activity restrictions was the primary treatment in the majority (97%) of those treated without surgery.

The BOSS cohort identified 'clinical irritability' of the hip and 'age' to be the only consistent factors that influenced treatment choices amongst surgeons. Surgery was rarely performed on those under five years old and occurred in more than half of those aged over eight years old. Surgeons operated more frequently on hips that they assessed to be 'irritable' or 'stiff'. The study confirmed the findings of prior literature by demonstrating a worse radiographic prognosis associated with increasing age, female sex, and greater radiographic collapse. However, the 'stiffness' of the hip did not appear to influence outcome. Furthermore, the study found no evidence to suggest that containment surgery improved outcomes. The results of the BOSS study prompted the commissioning brief by the NIHR Health and Technology Assessment (HTA) that has funded this study (NIHR commissioned funding call – 21/586 Management of Perthes' disease in children).

8.3 Research to date

The BOSS study is currently the most robust investigation into the treatment of Perthes' disease. There are no randomised controlled trials comparing treatments, and treatment decisions are largely dependent on the beliefs of the treating surgeon. Prior to the BOSS study, only two other cohort studies had sought to prospectively identify the outcomes of children with Perthes' disease [8, 9]. Each concluded that surgery had a small positive influence on Perthes' disease in specific subgroups of patients. However, each of these studies were subject to significant selection bias, and their findings were made from post-hoc analyses exposing them to type I error through multiple hypothesis testing and the reporting of subgroups with novel positive findings. The consistent findings were that children younger than 5 years old, males and those with less severe radiographic collapse, have marginally better radiological outcomes, regardless of treatment; though it was unclear how this translates into patient reported outcomes.

Alongside the BOSS cohort, OP Non-STOP study investigators have worked to understand the impact of Perthes' disease on the lives of children and their families. A mixed-methods study was undertaken that included 18 parents and 12 children to understand how the disease impacted day-to-day life. Profound effects of the disease on play, school attendance, sleep and physical and social wellbeing were identified [10]. This work led on to these themes being developed with clinicians, and the involvement of a larger group of children and parents throughout the world to create a Core Outcome Set (COS) for Perthes' disease [11]. In addition to the domains within the COS, surgeons emphasised the importance of radiological outcomes, particularly the femoral head shape, in trying to assess the likely longevity of the hip joint before the need for arthroplasty, as femoral head shape may be used to predict failure of a native hip joint.

8.4 Evidence why this research is needed now

The James Lind Priority Setting Partnership, and a separate priority setting exercise of the British Society of Children's Orthopaedic Surgery, has identified the need for surgery in Perthes' disease as one of the top research priorities in children's orthopaedic surgery [12, 13].

Furthermore, the BOSS study generated huge enthusiasm amongst clinicians and patient groups. This has created an excellent environment in which to definitively address the effectiveness of surgery in this childhood disease.

9 OBJECTIVES AND OUTCOME MEASURES

9.1 Aim

The aim of this randomised controlled superiority trial is to evaluate the clinical and cost-effectiveness of containment surgery compared to active containment amongst children aged between five and twelve years (inclusive) with Perthes' disease of the hip.

9.2 Primary objective and outcome measure

Table 6: Primary objective and outcome measure

| Objective | Outcome measure | Time point(s) of evaluation of this outcome measure (if applicable) | Data required | Source data (including location) |
|---------------------|------------------|---|------------------|---|
| To determine | PROMIS Mobility | Baseline and primary | PROMIS | Case |
| whether children | Computer Adapted | endpoint at 36 | mobility | report |
| treated with | Tool (CAT) | months post | score | Form |
| containment | | randomisation | | (entered |
| surgery have | | | | directly |
| better lower | | | | into the |
| extremity function | | | | REDCap |
| than children | | | | study |
| treated with active | | | | database) |
| containment | | | | |

9.3 Choice of primary outcome/justification for the follow-up period

Families were integral to inform the development of this study. Their input was taken along with evidence from the BOSS cohort, the qualitative work encompassing interviews with families and the developed core outcome set. All of this identified that physical function is most impacted amongst children with Perthes' disease and is therefore the most appropriate primary outcome in research.

The most appropriate outcome measure to test this domain has been identified to be the Patient-Reported Outcomes Measurement Information System (PROMIS) Mobility tool. In general, 'PROMIS scores' are a collection of patient-reported health status tools available for children and adults that were developed to be disease non-specific in collaboration with the US National Institute for Health (NIH). These tools can be administered to healthy children as well as to those with a variety of chronic health conditions. The PROMIS Paediatric item banks were developed using a strategic item generation methodology adopted by the PROMIS Network utilising item response theory. Field-testing occurred among 4129 children aged 8 – 17 years. Lower T-scores indicate a worse functional outcome. PROMIS is available in full (30 questions), short-form (8 questions) or as a CAT (average 8-questions). A CAT enables the answer from one question to inform the choice of the next and so each child could answer a distinct set of questions to arrive at their score.

A consensus-based standards for the selection of health measurement instruments (COSMIN) exercise advocated the use of the PROMIS tools in children's orthopaedic research, and experimental data demonstrates that PROMIS mobility strongly correlates with measured activity [14]. PROMIS-CATs have been used successfully in other NIHR-HTA trials led by members of the OP Non-STOP team, including SCIENCE, FORCE and CRAFFT [15].

The original version of the tool was a proxy (parent) reported version developed for children 8– 17 years old [16], which was subsequently validated in the younger population [17]. A self-reported version of the tool is available for use in older children. However, the PROMIS development team do not recommend combining the use of self-reported outcomes and proxy-reported outcomes. The proxy version of PROMIS Mobility is therefore the only outcome that covers the age spectrum within the study population. We will therefore seek a proxy report of PROMIS for all participants in this study. This approach will allow all outcomes to be combined in the analysis, irrespective of age.

The primary outcome measure for this study is Patient Reported Outcomes Measurement

Information System Mobility Score for Children (PROMIS-Mobility) at 3-years post randomisation. PROMIS-Mobility CAT is a validated tool to assess lower extremity function in children [18, 19].

The timepoint of 3-years reflects a typical time at which the inflammation and irritability associated with the disease process are subsiding, with ongoing restriction thereafter unlikely to notably improve spontaneously.

9.4 Secondary objectives and outcome measures

Table 7: Secondary objectives and outcome measures

| Objective | Outcome measure | Time point(s) of evaluation of this outcome measure (if applicable) | Data required | Source data (including location) |
|---|---|--|--------------------------------------|--|
| To compare lower extremity function in both groups | PROMIS Mobility CAT | Baseline and 3, 6, 9, 12, 18, 24, 30 and 36 months post randomisation | PROMIS mobility score | Case report Form (entered directly into the REDCap study database) |
| To compare pain levels in both groups | Wong Baker Faces Pain Scale | Baseline and 3, 6, 9, 12, 18, 24, 30 and 36 months post randomisation | Wong Baker Faces Pain Scale score | Case report Form (entered directly into the REDCap study database) |
| To compare Quality of Life, Activities of Daily Living, Sleep and Psychological Impact in both groups | CHU-9D Questionnaire | Baseline and 3, 6, 9m 12, 18, 24, 30 and 36 months post randomisation | CHU-9D score | Case report Form (entered directly into the REDCap study database) |
| To compare impact on family life in both groups | PROMIS family relationships tool | Baseline and 3, 6, 9, 12, 18, 24, 30 and 36 months post randomisation | PROMIS family relationships score | Case report Form (entered directly into the REDCap study database) |
| To compare educational participation in both groups | Non validated questionnaire on school absence | 3, 6, 9, 12, 18, 24, 30 and 36 months post randomisation | Days of school absence | Case report Form (entered directly into the REDCap study database) |

| Objective | Outcome measure | Time point(s) of evaluation of this outcome measure (if applicable) | Data required | Source data (including location) |
|---|--|--|--|--|
| To compare the complication rate, particularly considering the need for future operative interventions in both groups | Non validated questionnaire on complications | 6, 12, 18, and 36 months post randomisation | Frequency of pressure sores, non-union of the bone, wound or bone infection, major injury to nerves altering lower limb function, implant-related fracture, metalwork fracture/failure, need to remove/adjust metal implants, total hip arthroplasty (replacement) | Case report Form (entered directly into the REDCap study database) Medical notes |
| To estimate cost- effectiveness, from the UK NHS and Personal Social Services perspective in both groups | Non validated resource use questionnaire and CHU-9D | Baseline (CHU-9D only), 6, 9, 12, 18, 24, 30 and 36 months post randomisation | Resource use from hospital and out of pocket expenditure from families. CHU-9D score | Case report Form (entered directly into the REDCap study database) |
| To quantify the degree of residual deformity (waldenstrom grade and Stulberg classification) | Measured from routinely collected images of the hip or pelvis harvested from the picture archiving system. | An image of the hip or pelvis harvested from the picture archiving system within a 6 month timeframe of the primary outcome (36 months). | Routinely collected images of the hip or pelvis harvested from the picture archiving system. | Medical notes |

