17.1 Overview

Table 9 shows scheduled assessments for the study.

Table 9: Schedule of activities

| Assessments | Baseline | Intervention | 3 months post randomisation | 6 months post randomisation | 9 months post randomisation | 12 months post randomisation | 18 months post randomisation | 24 months post randomisation | 30 months post randomisation | 36 months post randomisation |
|---|----------|--------------|-----------------------------|-----------------------------|-----------------------------|------------------------------|------------------------------|------------------------------------|------------------------------|------------------------------|
| Demographics | * | | | | | | | | | |
| Status of Perthes' disease | * | | | | | | | | | |
| Randomisation | * | | | | | | | | | |
| Surgery / Best Practice Therapy Session | | * | | | | | | | | |
| PROMIS - Mobility | * | | * | * | * | * | * | * | * | * |
| Wong-Baker Faces Pain Scale | * | | * | * | * | * | * | * | * | * |
| CHU-9D | * | | * | * | * | * | * | * | * | * |
| PROMIS - Family Relationships | * | | * | * | * | * | * | * | * | * |
| Educational participation | | | * | * | * | * | * | * | * | * |
| Resource use Questionnaire | | | * | * | * | * | * | * | * | * |
| Complications (Additional care- participant reported) | | | | * | | * | * | | | * |
| Complications (site reported) | | | | | | | * | | | * |
| Collection of routinely available radiographs documenting the hip and pelvis appearance up to 36 months | | | | | | | | | | * |

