21.3 Expected adverse events

This is a low risk, pragmatic trial where both of the study interventions are in common use. For this trial, foreseeable AEs will not need to be reported immediately, but will be recorded on participant and site reported CRFs. They include the following (including the need for hospital admission and/or further unplanned surgery to manage these complications in either group):

The complications anticipated in the management of these patients (particularly considering readmission or subsequent surgery) include pressure sores, non-union of the bone, wound or bone infection, major injury to nerves altering lower limb function, implant-related fracture, metalwork fracture/failure, need to remove/adjust metal implants, total hip arthroplasty (replacement).

² Medical events that may jeopardise the participant or may require an intervention to prevent one of the above characteristics/consequences.

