21.5 Procedure for collecting safety events from sites/participants

These events will be recorded on patient-reported questionnaires and by the site investigators in the 'Complications' CRF if they become aware of such an event.

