23.2 Sample Size/Power calculations

172 participants providing data on the PROMIS Mobility Score for children at three years post randomisation (86 in each group) will provide 90% power to detect a difference in means of 5, assuming the standard deviation (SD) is 10 using a two group t-test with a 5% (2-sided) significance level. This is inflated to 216 participants (108 per arm) to allow for 20% attrition.

Raw scores of the PROMIS are translated into standardised T-scores with a population mean of 50 and an SD of 10.

The minimum clinically important difference (MCID) of PROMIS paediatric measures is generally 3.0-5.0 [29,30].

We discussed with children and families the size of the difference they would require to justify surgery, over optimised non-surgical containment. Given that surgery is a considerable intervention in the lives of the child and their family (i.e., the anaesthetic, the pain and scar, admission to hospital, the frequency of the requirement for a second procedure to removal metalwork, along with the lengthy

duration of immobilisation and recovery), families believed that the effect sought should be at the upper range of the MCID. Other studies have similarly highlighted that patients often seek greater effect sizes to warrant bigger surgical interventions than the established MCID [31].

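### No complications form is due between 18 and 36 months, although families already receive every other repeated questionnaire at 24 and 30 months

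*Protocol*

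**What the plan says.** The secondary objective in Protocol section 9.4 (Table 7) is "To compare the complication rate, particularly considering the need for future operative interventions in both groups". The outcome is a non-validated questionnaire at "6, 12, 18, and 36 months post randomisation", and the sources are the case report form and "Medical notes". The events counted include removal or adjustment of metal implants and hip replacement.

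Table 9 (section 17.1) has two rows for this outcome. The row beginning "Complications (Additional care- participant reported" is marked at 6, 12, 18 and 36 months. The row beginning "Complications (site reported" is marked at 18 and 36 months only. Appendix 1 and Appendix 2 follow the same schedule.

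Between scheduled forms, section 21.5 has sites complete the Complications form "if they become aware of such an event". Section 21.3 says that "foreseeable AEs will not need to be reported immediately", and its list covers the same complications as Table 7. Section 21.6 keeps the 24-hour route for unexpected, potentially related serious events.

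Section 23.2 reports why families wanted an effect at the top of the range of minimum important differences before accepting surgery. One of the burdens they weighed was "the frequency of the requirement for a second procedure to removal metalwork".

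**The concern.** The objective singles out later operations, and families weighed a second procedure when they set the benefit that would justify surgery. Yet from month 18 to month 36 nobody is scheduled to ask about complications. Families are in contact at 24 and 30 months and answer on mobility, pain, quality of life, family relationships, education and resource use. Complications is the only repeated participant questionnaire left out at both points, and no reason is given.

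Two things are at stake. The first is accuracy: a family that reaches month 36 must recall 18 months on one form. The second is completeness: a family that answers at 24 or 30 months and is then lost was reachable but was never asked. Both would tend to under-count late events in an outcome that is read against any functional gain from surgery.

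**Working it through.** **1. The plan's own figures.** Section 23.2 uses a difference of 5, SD 10, 90% power and two-sided 5%. The two-sample t-test gives 85.03, so 86 per group (power 0.903). Allowing for 20% attrition, 86 / 0.80 = 107.5, so 108 per arm and 216 in all. These figures reproduce. They serve here only as a denominator.

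**2. Schedule side by side (Table 9, Appendix 2).**

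| Months after randomisation | 3 | 6 | 9 | 12 | 18 | 24 | 30 | 36 |
|---|---|---|---|---|---|---|---|---|
| All other repeated participant questionnaires | yes | yes | yes | yes | yes | yes | yes | yes |
| Participant complications | – | yes | – | yes | yes | – | – | yes |
| Site complications | – | – | – | – | yes | – | – | yes |

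The intervals between participant complications forms, counted from randomisation, are 6, 6, 6 and 18 months. Leaving out months 3 and 9 never opens a gap above 6 months; leaving out 24 and 30 does. The longest gap is 36 − 18 = 18 months, and 18 / 36 is half of follow-up. With forms at 24 and 30 the intervals are all 6 months, and the number of participant forms rises from 4 to 6.

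**3. Children who were reachable but not asked.** The 20% allowance in section 23.2 is for the 36-month PROMIS Mobility score. Assume the same loss for the 36-month complications form: 0.20 × 216 = 43.2. Let p be the share of these children who answered at 24 or 30 months. The protocol gives no value for p, so the number is p × 43.2:

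- p = 0: 0 children
- p = 0.25: 43.2 × 0.25 = 10.8, about 11
- p = 0.50: 43.2 × 0.50 = 21.6, about 22
- p = 1: about 43

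These are children who lose participant-reported complications after month 18. They are not children with no complications data, because section 17.6 lets a family stop questionnaires and still allow routine record data. Under its other option, which stops both, the 36-month notes route closes as well.

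**4. Scheduled site forms during recruitment (context only).** By month 30 only children randomised in the first 12 months can have reached the 18-month site form. Their number is 0.35 × (sum of sites open in each of months 1 to 12). The speed of site opening within the pilot is not stated, so three patterns are assumed:

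- 15 sites from the start: 0.35 × 15 × 12 = 63, and 63 / 216 = 29%
- 5 rising to 15 over six months, then 15: 0.35 × (60 + 90) = 52.5, and 52.5 / 216 = 24%
- linear rise to 15 over twelve months: 0.35 × 97.5 = 34.1, and 34.1 / 216 = 16%

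The pilot target of 50 gives 50 / 216 = 23%.

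For the 6-month participant form, count those randomised by month 24. Months 13 to 18, rising from 15 to 28 sites, add 0.35 × 135.5 = 47.4. Months 19 to 24 at 28 sites add 0.35 × 168 = 58.8. The totals run from 34.1 + 106.2, about 140 (65%), to 63 + 106.2, about 169 (78%).

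**The case against.** The other side has a good deal to say. The tables and appendices agree, so nothing here is contradictory. Medical notes are a listed source, and Appendix 2 has the local team review complications and serious events at 36 months. Resource use at 24 and 30 months covers hospital care, so a re-operation could surface there. Complications are only summarised by arm (section 23.3.2), in a trial the protocol regards as low risk.

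Much of this stands, and it rules out two stronger readings. A reader might infer that late re-operations rest on recall alone. They do not, since the notes review covers the same interval. A reader might also infer that the data and safety monitoring committee depends mainly on lay reports during recruitment. Scheduled site forms will indeed have been reached by only about 16% to 29% of participants by month 30. But sites may file a Complications form at any time, the surgery form records intra-operative complications, unexpected related serious events arrive within 24 hours, and participant forms start at 6 months. The documents do not support that inference.

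What the objection leaves open is narrower. The notes review happens once and looks back, and the protocol is silent on whether it reaches care given outside the recruiting site. Reporting between forms is passive. Resource use is collected for costing and is not named in Table 7 as a source for complications. None of these routes asks the family about complications while it is still answering questionnaires.

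**Conclusion.** The point holds as an avoidable design weakness. For half of follow-up the complications outcome has no scheduled form until month 36, and the family contacts that could fill the gap already exist.

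The size is an 18-month gap where 6 months is available, and between 0 and about 43 of 216 children whose late participant-reported complications would be lost although the family answered at 24 or 30 months. The upper figure assumes that the 20% attrition allowance carries over to the 36-month complications form and that every child lost had answered at 24 or 30 months. It should be read as a ceiling, partly offset by medical notes where record access continues.

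The number of missed events cannot be estimated, because the protocol gives no complication rate. Under-counting that differs by arm is conceivable, but nothing in the document allows it to be sized, and the conclusion does not rest on it.

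**What to change.** In Table 7, Table 9 and Appendix 2, add the existing participant complications form at 24 and 30 months, so that the time points become 6, 12, 18, 24, 30 and 36 months.

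The cost is a change to the schedule wording and the REDCap set-up, and a few extra questions for families at two contacts that already take place. The longest gap between participant forms falls from 18 to 6 months. A child who answers at 24 or 30 months and is then lost would have complications recorded up to that contact; the time after it would still depend on the notes.

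Mandatory site notes checks at 6 and 12 months are not part of this recommendation. They would add up to 2 × 216 = 432 checks, at contacts where Appendix 2 has the local team record only the date, and participant complications forms are already collected at both points.
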